## INVESTIGATOR STUDY PLAN - REQUIRED

revising the therapist companion guide. We will then develop a training program for *Signs of Safety* and certify four study clinicians.

We propose to conduct a **two-arm pilot RCT of *Signs of Safety***. We aim to enroll 60 Deaf adults with past-month PTSD and past-month alcohol consumption to participate in 12 weekly individual treatment sessions. The pilot RCT will compare the 12-session protocol of *Seeking Safety + Signs of Safety* toolkit with an assessment-only waitlist control. Across conditions, assessment will occur at baseline, week 4, week 8, immediate post-treatment/week 12, and one-month follow-up/week 16. We will analyze key aspects of feasibility for both study arms (e.g., recruitment, retention, assessment process). Primary clinical outcomes at immediate post-treatment and one-month follow-up are past 30-day alcohol use frequency/quantity and past 30-day PTSD severity. Exploratory analyses will be conducted to examine potential moderators and mediators of change (e.g., motivation for treatment, provider cultural competency, coping skills, self-compassion, understanding of health information) leading to positive outcome. Results from this study will produce feasibility and preliminary efficacy data to support for a full-scale RCT to evaluate *Signs of Safety*, and a community-engaged model for conducting RCTs with Deaf participants.

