**Table 3: Clinical Outcome Measures**

Variable	Measure (primary outcome measures noted in bold font)	Time Point					
		Screen	Baseline/ Pre-TX	Week 4	Week 8	Week 12/ Post-TX	1-month Follow-up
Alcohol Use and Craving	AUD Identification Test (AUDIT)	X					
	Alcohol Timeline Followback		X	X	X	X	X
	Comprehensive Effects of Alcohol Scale - Brief		X	X	X	X	X
	Penn Alcohol Craving Scale (PACS)		X	X	X	X	X
PTSD	PTSD Checklist for DSM-5 (PCL-5)	X	X	X	X	X	X
	Trauma Symptom Checklist – 40 (TSC-40)		X			X	X
Behavioral Health	Behavior and Symptom Identification Scale (BASIS-24)		X			X	X
Mediators and Moderators of Change	Coping Self-Efficacy Scale		X	X	X	X	X
	Self-Compassion Scale – Short Form		X	X	X	X	X
	Ask, Understand, Remember Assessment (AURA)		X	X	X	X	X
	Stages of Change Readiness and Treatment Eagerness Scale (SOCRATES 8A)		X			X	X
	Healthcare Provider Cultural Competency		X			X	X

**Identification of serious psychiatric problem.** If at any time a participant is identified as having a serious psychiatric problem that requires a higher level of care than our study can provide, this concern will be immediately reported to the PI, who will provide referral and bridging to appropriate treatment options for stabilization. Once stabilized, the participant will have the option to return to our study.

**Clinical emergencies.** Study clinicians and Study Assessor will contact 911 in the event of a dangerous situation (or the PI for less urgent clinical crises), and will complete adverse events

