## INVESTIGATOR STUDY PLAN - REQUIRED

*administer a client satisfaction measure that will unblind the Co-I to which subjects are in the waitlist control group.)*

**Intervention:** Participants randomized to receive the intervention will be provided weekly individual treatment with one of four ASL-fluent study clinicians, based on preferred location and transportation needs. Each participant in this condition will receive 12 one-hour sessions of treatment. The maximum length of treatment will be capped at six months and the total number of completed sessions will be tracked as a measure of participant adherence. Therapists will treat an approximately equal percentage of participants, in order to minimize confounding of therapist effect and study site on treatment outcome.

Treatment sessions will be provided in each study clinician's private practice office, in direct response to findings from the PI's NIDCD R21, which revealed Deaf people's communal fear of academic research settings due to a long history of mistreatment by doctors and biomedical researchers (e.g., eugenics) (Anderson, Wolf Craig, & Ziedonis, 2016; Anderson et al., 2018; Anderson, Wolf Craig, & Ziedonis, 2017; McKee, Schlehofer, & Thew, 2013; Lane, 2005). As such, study therapists must be independently licensed in MA and will take on professional liability for the cases that they see. Study therapists will be compensated \$80 a session – a rate that is comparable to the average insurance reimbursement for individual therapy sessions with Deaf clients. Proof of sufficient liability insurance will be obtained from each study therapist prior to beginning the RCT.

**Waitlist Control:** Following the final assessment at 16 weeks, waitlist control participants will be offered the opportunity to receive the 12-session *Seeking Safety + Signs of Safety* protocol. This 16 week waiting period is equivalent to the current waitlist to receive psychotherapy services through the PI's outpatient clinic. Participants who are randomized to the waitlist, but express immediate need for services during the waitlist period will be provided referral to non-study treatment options (i.e., supportive psychotherapy provided either directly in ASL or with an ASL interpreter) and subsequently coded as a non-retained waitlist participant.

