**Assessments.** Using measures validated in the general population, we will assess clinical outcomes and mechanisms of change at baseline, two within-treatment time points (after session 4 and 8), immediate post-treatment (within one week after session 12), and one-month follow-up. The Study Assessor, blind to study condition, will administer assessments as structured ASL interviews via videophone. (*Note: the Study Assessor will remain blind to study condition until the end of the post-treatment assessment, at which point she will administer a client satisfaction measure that will unblind the Co-I to which subjects are in the waitlist control group.*) Any Likert-scale-type questionnaires that are administered during the study interview will be presented directly in American Sign Language; the interviewer will also display a visual aid of the response options to assist participants in keeping track of changing Likert scales between various measures.

Compared to in-person assessments, our proposed method of remote videophone assessment is more responsive to Deaf people's transportation barriers, financial barriers, and technology preferences. This videophone method was used successfully in the *Signs of Safety* one-arm pilot study, as well as other previous studies with Deaf individuals. Participants will be compensated

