**Table 3: Feasibility Measures**

Component	Feasibility Quantification
Client Satisfaction	- Seeking Safety End of Session Questionnaire * - Seeking Safety End of Treatment Questionnaire * - Client Satisfaction Questionnaire (post-TX)
Treatment Fidelity	- Rates of therapist integrity to the experimental condition
Participant Adherence	- Treatment receipt (i.e., number of sessions completed, comprehension of session content) - Rates of participants' treatment enactment (i.e., completing "homework" between sessions)
Assessment Process	- Proportion of planned ratings completed - Duration of assessment call - Psychometrics of clinical outcome measures

\*Measures that include open-ended items for qualitative data analysis.

**Measures of clinical outcome, moderators, and mediators:** Using measures validated in the general population, we will assess clinical outcomes and mechanisms of change at baseline, two within-treatment time points (week 4 and 8), immediate post-treatment (within one week after session 12), and one-month follow-up. We will report internal consistency of all measures in our study sample when administered in ASL format, compared with the general population.

Measures of **clinical outcome** are: the *Alcohol Timeline Followback*, which assesses daily drinking frequency and quantity for a selected range of 30 to 360 days (we will use 30 days); the *Comprehensive Effects of Alcohol Scale – Brief Version*, a 15-item measure of positive/negative expectancies and valuations of various possible consequences of drinking; the *Penn Alcohol Craving Scale (PACS)*, a 5-item instrument assesses study participants' self-report craving levels for alcohol; the *PTSD Checklist for DSM-5 (PCL-5)*, a 20-item measure of DSM-5 PTSD symptoms that is reliably used to monitor symptom change; the *Trauma Symptom Checklist – 40 (TSC-40)*, a 40-item measure of the long-term effects of complex trauma; and the *Behavior and*

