**Analytic plan for preliminary clinical outcomes.** We will compare treatment arms using two primary clinical outcomes at immediate post-treatment and one-month follow-up: (1) past 30-day alcohol use frequency/quantity (from *Alcohol Timeline Followback*); and, (2) past 30-day PTSD severity (from *PCL-5*). For **alcohol use**, outcome variables are: % drinking days per week (i.e., days with 1+ drink); % binge drinking days per week (i.e., days with 5+ drinks for men, 4+ for women); and mean number of drinks per week. These variables will be calculated from daily data collected with the *Alcohol Timeline Followback* for 30 days (4 weeks) prior to the last drink before baseline assessment, throughout the 12-week intervention or waitlist period, and throughout the one-month follow up period. Such a weekly measure will allow for estimation of changes per weekly intervention session in the experimental condition as compared to waitlist control.

Our initial unadjusted group comparisons at immediate post-treatment/week 12 and at the end of the one-month follow-up period/week 16 will use a standard t-test (or Wilcoxon non-parametric test, depending on the outcome distribution). Below, we describe models for analyzing adjusted group differences and for analyzing the longitudinal data. We acknowledge that, with the small sample size of this feasibility study, the following models may be optimistic in terms of their capability to reliably estimate and to test interactions. However, they will provide insight into possible effect sizes for planning the larger clinical trial.

We will first compare differences in weekly drinking between the two study conditions at pre-, during, and post- intervention periods using mixed effects models (Model 1):

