### **23. RESOURCES AVAILABLE**

**PI:** The Principal Investigator will be responsible for the overall administration and coordination of the proposed research project, including participant recruitment, informed consent procedures, eligibility screening, data collection, data analysis, and dissemination of results. Qualifications include: licensed psychologist, expertise in Deaf community health and Deaf clinical research; ASL fluency.

**Study Assessor:** The Study Assessor will be responsible for conducting all outcome assessments. Qualifications include: expertise in Deaf community health and Deaf clinical research; ASL fluency; proficient interview skills.

**Co-I/AUD Research Consultant:** The Co-I/AUD Research Consultant is an expert in AUD research and will provide guidance and consultation on AUD RCT methodological design.

**Addiction Psychiatrist:** The Addiction Psychiatrist will be responsible for responding to on-call phone consultations regarding medical concerns (e.g., withdrawal symptoms).

**Biostatistician:** The Biostatistician will oversee all statistical aspects of the study (e.g., data management, analysis) and supervising the database developer and statistical analyst.

**Statistical Analyst:** The Statistical Analyst will work under the Biostatistician to assist with all statistical aspects of the study (e.g., data management, analysis).

**Research Coordinator:** The research coordinator will be responsible for assisting the PI's with the overall administration and coordination of the proposed research project, including participant recruitment, data collection, data analysis, and dissemination of results. Qualifications include: 2 years of experience working as a UMMS Research Coordinator.

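### The Study Assessor is unblinded by design at the end of the post-treatment visit, before she collects the one-month primary outcomes; moving one questionnaire removes this planned unblinding.

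*Combined protocol and SAP*

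**What the plan says.** Section 11 describes assessor blinding in general terms under Assessments: "The Study Assessor, blind to study condition, will administer assessments as structured ASL interviews via videophone". A note there, repeated under Study Conditions, limits it. The assessor will "remain blind to study condition until the end of the post-treatment assessment, at which point she will administer a client satisfaction measure". The note describes the effect of that step: she will "administer a client satisfaction measure that will unblind the Co-I to which subjects are in the waitlist control group". Knowing who is on the waitlist identifies the treated participants by elimination.

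The feasibility table in section 11 schedules the "Client Satisfaction Questionnaire" at post-treatment only. Section 23 states: "The Study Assessor will be responsible for conducting all outcome assessments". It names no second assessor for follow-up.

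The later visit is a primary time point. Section 4: "Primary clinical outcomes at immediate post-treatment and one-month follow-up are past 30-day alcohol use frequency/quantity and past 30-day PTSD severity". Section 13: "We will compare treatment arms using two primary clinical outcomes at immediate post-treatment and one-month follow-up", with a t-test or Wilcoxon test planned at both week 12 and week 16. The clinical outcome table in section 10 schedules the Timeline Followback and the PCL-5, both marked as primary, at the one-month visit.

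**The concern.** The plan chose to blind the assessor, then gives up that protection before one of its two primary time points, for the sake of one feasibility questionnaire. Both primary measures are live signed interviews. The Timeline Followback reconstructs daily drinking and the PCL-5 items are presented by the interviewer, so prompting or clarification could differ once she knows the arm.

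A shift common to both arms cancels in the comparison. A shift that differs by known arm does not, and it could favour either arm. The terms exposed are the follow-up-by-arm coefficient (b5) in Model 1, the last condition-by-time term in Model 3, and the unadjusted week-16 tests. Because blinding changes between the two primary visits, a difference between the week-12 and week-16 effects could also partly reflect that change.

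A related point needs checking. The "Healthcare Provider Cultural Competency" items are scheduled at post-treatment with no stated place in the order. If the answers show whether a participant has a study clinician, the arm could be revealed before the week-12 outcomes are complete.

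**Working it through.** **Who is unblinded before follow-up.** Sections 6 and 25 give 60 enrolled and 75% retained to post-treatment: 60 × 0.75 = 45, which reproduces the plan's figure. These are the participants who reach the unblinding step. Someone who misses post-treatment but is reached at follow-up, as section 11 allows, is not unblinded by it.

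**Which comparisons are affected.** Section 13 names three alcohol variables (drinking days, binge days, mean drinks) and the PCL-5 total, each at two time points: (3 + 1) × 2 = 8 comparisons, of which 4 are at follow-up. Counting only the two named outcomes gives 2 × 2 = 4, of which 2 are at follow-up. The share is half either way.

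**Sequence.**

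| Step | Source | Assessor's status |
|---|---|---|
| Post-treatment outcomes | Section 11 | Blind |
| Satisfaction measure at the end of that visit | Section 11 notes | Unblinded |
| One-month Timeline Followback and PCL-5 | Table in section 10; sections 13 and 23 | Same assessor; no re-blinding described |

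**Illustration of what a differential shift would do.** The plan gives no size for assessor bias. The inputs from the plan are the PCL-5 SD of 21.2 and 22 completers per arm (section 13). The assumptions are a two-sided 5% t-test, no true effect, and a differential shift of 2 to 5 points in either direction.

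- Shift in SD units: 2/21.2 = 0.094; 5/21.2 = 0.236.
- Standard error of the difference: 21.2 × √(2/n).
- Rejection rate: the noncentral t probability of exceeding the critical value in either tail, with noncentrality equal to shift/SE.

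| n per arm | SE (points) | df | Rejects at 2 points | Rejects at 5 points |
|---|---|---|---|---|
| 18 | 7.07 | 34 | 5.9% | 10.6% |
| 22 | 6.39 | 42 | 6.1% | 11.9% |
| 30 | 5.47 | 58 | 6.5% | 14.6% |

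The plan states no follow-up n. The 18 assumes 20% further loss after week 12 (45 × 0.80 = 36 in total). The 30 assumes that everyone randomized is reached. For scale, the 95% confidence-interval half-width at 22 per arm is 2.018 × 6.39 = 12.9 points, so a 2-point shift is negligible beside sampling error.

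**The case against.** The unblinding is disclosed, and it is placed after the week-12 measures, which protects that contrast provided the satisfaction measure is given last. This is a feasibility pilot whose clinical results are called preliminary, and section 13 says a clinically significant effect should be used to plan the full-scale trial, so no effect on that trial's size is claimed. Participants know their arm throughout, both outcomes are structured self-reports, and the Likert response options are displayed. The added bias may therefore be small, and the 2 to 5 points have no source in the plan; 5 points is half of what section 13 treats as clinically significant. All of this stands, and it limits the point to an avoidable weakness rather than a demonstrated distortion.

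Moving one questionnaire also does not guarantee blinding. Participants may disclose their arm. Visit timing is a cue as well: section 11 ties treated participants' assessments to sessions 4, 8 and 12, with treatment allowed to run to six months, while control assessments fall at fixed weeks. The change removes the planned disclosure and nothing more.

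The cultural-competency concern is conditional. The scale is also given at baseline, before randomization, so it must be answerable without a study clinician. It needs checking, not presuming.

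Finally, satisfaction is a listed feasibility component, and delaying it has a cost. That cost is real but modest, and the alternatives below keep the timing.

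None of this restores blinding at follow-up or explains why the questionnaire must come before the week-16 outcomes.

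**Conclusion.** The concern holds and should be fixed. As written, the plan reveals study arm to the person who collects the one-month primary outcomes for every post-treatment completer, about 45 of 60 at planned retention, and half of the primary arm comparisons are exposed. This follows from the text and needs no assumption about bias.

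The size and direction of any bias are unknown. The rejection rates (5.9% to 14.6% across 18 to 30 per arm) rest wholly on the assumed shifts and a two-sided 5% level, and the low end is negligible. The recommendation rests on avoidability at a primary time point. With the satisfaction measure moved, the number unblinded by that step before follow-up outcomes falls from about 45 to 0.

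**What to change.** **Preferred.** Move the satisfaction questionnaire to the very end of the one-month call, after all outcome measures. Amend both notes in section 11 so that the assessor stays blind until the follow-up outcomes are recorded. Waitlist participants are offered the intervention only after the week-16 assessment, so the arms are still as randomized at that call. This needs a protocol amendment but no new visit, measure or staff. It costs about four weeks of extra recall and the responses of those who complete post-treatment but not follow-up. The plan gives no figure for that loss; at an assumed 0% to 20%, it is 0 to 9 of about 45 (45 × 0.20 = 9). End-of-session questionnaires still capture satisfaction during treatment.

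**If post-treatment timing must stay.** Either of these routes keeps the timing and those responses:

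- An ASL-fluent team member who does not assess outcomes gives the measure. This means about 45 (at most 60) short contacts if both arms complete it, or about 22 to 30 if only treated participants do. Using the Exit Interviewer would require amending section 23, which confines that role to after all study procedures.
- Participants complete it themselves in REDCap, as section 26 already provides for the end-of-session questionnaire, with results hidden from the assessor. ASL accessibility would need checking.

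**In the same amendment.**

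- Reconcile the roles: the note says the measure unblinds the Co-I, whom section 23 lists separately from the Study Assessor.
- Check whether the cultural-competency items, or the End of Treatment Questionnaire if the assessor gives it, reveal arm. If so, keep them away from her until the follow-up outcomes are complete. For the cultural-competency scale, that means either another route at week 12 or losing that measurement, since it is already scheduled at follow-up.

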## INVESTIGATOR STUDY PLAN - REQUIRED

\$25 at each assessment time point (1 hour for baseline, 30 minutes for follow-up) via a Visa gift card sent to the mailing address of their choice. Participants not retained in treatment will be contacted for follow-up assessments at each scheduled time point for intent-to-treat analyses and examination of potential biases due to non-adherence.

In the control condition, assessment will occur at baseline, week 4, week 8, week 12 (to approximate immediate post-treatment), and week 16 (to approximate one-month follow-up). Such repeated assessment in the control arm will allow us to quantify and control for participants' natural change over time and assessment reactivity.

**Feasibility measures:** We will collect data on recruitment, retention, and other key aspects of feasibility (Table 3). We will augment client satisfaction measures with questions specific to *Signs of Safety*. All intervention sessions will be videotaped, with 25% (3 sessions per participant) rated for fidelity on an ongoing basis by the Fidelity Consultant To quickly correct fidelity concerns, capture fidelity throughout the treatment process, and evaluate impact of site differences on study findings, one tape will be randomly selected from sessions 1 - 4; one from 5 - 8; and one from 9 - 12. Sessions will be rated with the *Seeking Safety Adherence Scale* plus the *Signs of Safety Fidelity Scale*.

**Table 3: Feasibility Measures**

Component	Feasibility Quantification
Client Satisfaction	- Seeking Safety End of Session Questionnaire * - Seeking Safety End of Treatment Questionnaire * - Client Satisfaction Questionnaire (post-TX)
Treatment Fidelity	- Rates of therapist integrity to the experimental condition
Participant Adherence	- Treatment receipt (i.e., number of sessions completed, comprehension of session content) - Rates of participants' treatment enactment (i.e., completing "homework" between sessions)
Assessment Process	- Proportion of planned ratings completed - Duration of assessment call - Psychometrics of clinical outcome measures

\*Measures that include open-ended items for qualitative data analysis.

**Measures of clinical outcome, moderators, and mediators:** Using measures validated in the general population, we will assess clinical outcomes and mechanisms of change at baseline, two within-treatment time points (week 4 and 8), immediate post-treatment (within one week after session 12), and one-month follow-up. We will report internal consistency of all measures in our study sample when administered in ASL format, compared with the general population.

Measures of **clinical outcome** are: the *Alcohol Timeline Followback*, which assesses daily drinking frequency and quantity for a selected range of 30 to 360 days (we will use 30 days); the *Comprehensive Effects of Alcohol Scale – Brief Version*, a 15-item measure of positive/negative expectancies and valuations of various possible consequences of drinking; the *Penn Alcohol Craving Scale (PACS)*, a 5-item instrument assesses study participants' self-report craving levels for alcohol; the *PTSD Checklist for DSM-5 (PCL-5)*, a 20-item measure of DSM-5 PTSD symptoms that is reliably used to monitor symptom change; the *Trauma Symptom Checklist – 40 (TSC-40)*, a 40-item measure of the long-term effects of complex trauma; and the *Behavior and*

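### The Timeline Followback look-back is fixed at 30 days with no rule for longer gaps between completed visits, so the weekly drinking models lose days that a longer recall at the next visit could collect

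*Combined protocol and SAP*

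**What the plan says.** In Section 11 (measures of clinical outcome, moderators, and mediators), the Timeline Followback is the instrument "which assesses daily drinking frequency and quantity for a selected range of 30 to 360 days (we will use 30 days". No section lengthens that window after a late or missed visit.

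Section 13 (analytic plan for preliminary clinical outcomes) computes percent drinking days, percent binge days and mean drinks per week from daily data. After baseline, these data are to run "throughout the 12-week intervention or waitlist period, and throughout the one-month follow up period". The stated purpose is that "Such a weekly measure will allow for estimation of changes per weekly intervention session" in the treated arm against waitlist. Section 13 relies on mixed models that use all available data under missing at random.

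Visit timing is given in two ways. Section 11 (Assessments) has "two within-treatment time points (after session 4 and 8), immediate post-treatment (within one week after session 12), and one-month follow-up", and Section 14 also counts by session. The later measures paragraph of Section 11 has "two within-treatment time points (week 4 and 8), immediate post-treatment (within one week after session 12), and one-month follow-up". Section 4 and the clinical outcome table in Section 10 use weeks for both arms, and Section 11 fixes control visits at weeks 4, 8, 12 and 16. For the treated arm, Section 11 (Intervention) adds: "The maximum length of treatment will be capped at six months".

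**The concern.** The analysis wants a continuous calendar, while the instrument rule supplies separate 30-day windows. The two agree only while consecutive completed visits are at most 30 days apart, and the nominal spacing leaves two days of slack. The plan itself foresees longer gaps. Treatment may stretch to six months, stabilized participants may return, people who leave treatment are still contacted for assessment, and retention is projected at 75%.

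At stake are the weekly series behind Models 1 and 2 and the effect sizes they are meant to supply for a larger trial. The loss could also depend on the outcome. Section 14 has clinicians stop and reschedule a session when a participant arrives under the influence. In the treated arm, drinking can therefore delay session 12 and push drinking days beyond the recall window. That strains the missing-at-random assumption for data the next interview could have collected.

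**Working it through.** **Inputs.** Look-back of 30 days (Section 11); nominal visits at days 28, 56, 84 and 112 (Sections 4, 10 and 11); six-month cap, taken here as 26 weeks = 182 days (Section 11).

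**Formula.** For a gap of G days between completed visits, days not collected = max(0, G − 30).

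**Planned schedule.** Each gap is 28 days, so max(0, 28 − 30) = 0. All 112 post-baseline days are covered, with two days of overlap per interval.

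**Late or missed visits, either arm.**
- 1 or 2 days late: G = 29 or 30, loss 0.
- 3 days late: G = 31, loss 1.
- 7 days late: G = 35, loss 5.
- Week 4, 8 or 12 missed and the next visit completed: G = 56, loss 56 − 30 = 26 of 112 days (23%).
- Weeks 4 and 8 both missed: G = 84, loss 54.
- Week 16 missed: its 28 days are lost whatever the look-back rule.

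**Treated arm, session 12 delayed to day T.** Both columns assume that the post-treatment visit is on the day of session 12 and that no visit is missed.
- Session-anchored, evenly spaced: three gaps of T/3, so loss = T − 90 once T exceeds 90.
- Interim visits at weeks 4 and 8: the whole delay falls in the last gap, so loss = T − 56 − 30 = T − 86 once T exceeds 86.

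| Session 12 at | T (days) | Session-anchored | Interim visits at weeks 4 and 8 |
|---|---|---|---|
| Week 12 | 84 | 0 | 0 |
| Week 16 | 112 | 22 (20%) | 26 (23%) |
| Week 22 | 154 | 64 (42%) | 68 (44%) |
| Week 26 | 182 | 92 (51%) | 96 (53%) |

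The week-22 row applies if the six-month limit on participation in Section 9 includes the follow-up month. If all treated-arm visits are at fixed weeks, as Section 4 can be read, this route disappears.

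**After the fix.** Loss is 0 for every late visit and for every missed visit followed by a completed one. The longest recall, with all interim visits missed and treatment at the cap, is about 182 + 7 + 30 = 219 days, inside the quoted 360-day range.

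**The case against.** A reader might infer that a 30-day look-back cannot deliver the daily record at all, or that any late visit leaves a hole. Neither is so. The planned schedule is fully covered, and a delay of one or two days costs nothing.

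A reader might also infer that the loss falls mostly on the treated arm. The documents do not establish this. A missed visit costs the same in both arms, and projected retention is not split by arm. Waitlist participants referred elsewhere for immediate need are coded as non-retained, which is a loss route specific to controls. The delay figures need slow treatment, six months is a cap and not an expectation, and several sections give calendar weeks. Nor does the one-week allowance after session 12 by itself create a hole. If weekly sessions start on day 0, session 12 is on day 77 and a visit seven days later is on day 84, which is on time.

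It is also fair that the mixed models do not need every week, and that the past 30-day outcome at a completed post-treatment or follow-up visit is directly covered. Section 13 itself warns that the models may be optimistic at this sample size. The lost days are not beyond recovery in principle, since the instrument reaches 360 days. The session check-ins in Section 14 do record weekly alcohol use. However, they exist only in the treated arm, are described for safety monitoring, are not stated to be daily and are not named as an analysis source. Using them would measure the two arms differently.

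These points limit the size and reach of the problem. They do not supply the missing rule for gaps over 30 days.

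**Conclusion.** The concern holds in a limited form. Followed exactly, the plan discards drinking days that the next interview could collect whenever completed visits are more than 30 days apart. The cost is 26 days for one missed visit followed by a completed one, in either arm, and 5 days for a 35-day gap. The treated arm has one additional route while its post-treatment visit is tied to session 12 and controls are seen at fixed weeks. That route would cost 22 to 26 of 112 days if session 12 falls at week 16, and 92 to 96 of 182 at the cap.

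The treated-arm figures are illustrations, because the documents give no distribution of treatment length or visit delay. It is tempting to add that drinking is heavier in the lost weeks, but no figure in the documents shows that. What they show is one mechanism by which drinking can delay a session. The consequence is confined to the weekly longitudinal models and their missing-at-random assumption. This is a worthwhile, inexpensive correction and not a threat to the comparison of past 30-day use at completed visits.

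**What to change.** - **Section 11, measures paragraph:** state that each post-baseline Timeline Followback covers the longer of 30 days or all days since the last completed Timeline Followback.
- **Section 13:** count each calendar day once, and say which report is kept where windows overlap. Derive the past 30-day outcomes from the same calendar.
- **Baseline window:** make the two sections agree. Section 13 anchors it to the last drink before the baseline assessment, while Section 11 says only 30 days.
- **Visit timing:** reconcile the session-based and calendar-based statements in Sections 4, 10, 11 and 14.
- **Recall length:** record, for each day, how long before the interview it fell, and run a sensitivity analysis on it.

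**Cost.** The wording change is small and adds no visit. Interviews and recall become longer after gaps only, but the extreme of about 219 days would be hard to fit into the 30 minutes planned for a follow-up assessment. Long recall may also be more common in the treated arm, which is why recall length should be recorded. The fix does not recover the period before a final visit that is never completed.
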